Thus, the objective of this national quality improvement project is to develop an adaptive strategy to improve implementation of VA Risk ID to fidelity. Using a sequential multiple assignment randomized trial (SMART) design, two evidence-based implementation strategies will be evaluated: 1) Audit and Feedback (A/F); 2) A/F plus External Facilitation (A/F+EF). We will evaluate these strategies across several domains based on the RE-AIM OUEST mixed methods framework⁹. In addition to focusing on implementation outcomes, such as the impact of these strategies on implementation of VA Risk ID to fidelity, and potential barriers to adopting these strategies, we will also examine the impact of the clinical innovation (i.e., VA Risk ID) on patient-level outcomes. **Primary Aim:** Among sites that do not meet the benchmark for adequate performance (i.e., completion of secondary screening and CSRE for 80% or more of eligible patients) following 6 months of Implementation as Usual (IAU), does the addition of A/F for 10 months significantly improve scores on VA Risk ID performance measures compared to IAU alone? Secondary Aims: 1) Among sites that continue to not meet the benchmark for adequate implementation after 10 months of A/F, does the addition of EF significantly improve scores on VA Risk ID performance measures compared to A/F alone? 2) Among sites that meet the benchmark following A/F alone, is performance maintained following discontinuation of A/F? Outcomes for primary and secondary aims will use clinical performance measures extracted from VA's External Peer Review Program (EPRP) that reflect key practice elements of VA Risk ID: completion of the primary suicide screen, timely completion of the secondary suicide screen and timely completion of the CSRE. Exploratory Aims: 1) Examine the extent to which VA Risk ID is reaching the intended population and compare the characteristics of Veterans reached to all Veterans eligible for screening: 2) Examine contextual factors that may impact the a) implementation of VA Risk ID to fidelity and b) adoption of the implementation interventions. 3) Examine whether Veterans who receive the CSRE are more likely to receive a safety plan than Veterans who screen positive on the primary screen only. **This project directly**

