C1. Evaluation Framework. RE-AIM QUEST⁹ will provide an overarching framework for testing the impact of the proposed adaptive implementation strategy. RE-AIM QUEST expands RE-AIM by allowing investigators to understand not only whether Reach, Effectiveness, Adoption, Implementation and

Maintenance vary across sites and conditions, but also how and why these variations occur⁹. Moreover, RE-AIM was selected because of its ability to provide an approach to evaluation that focuses both on the impact of the implementation interventions and the impact of the clinical innovation (Table 1).

RE-AIM Domain	Operationalization	Data Sources			
Level of Evaluation: Clinical Innovation					
Reach	The absolute number and representativeness of Veterans that received the primary, secondary screens and CSRE.	Administrative (CDW) Data			
Effectiveness	Whether Veterans who receive the CSRE are more likely to receive a safety plan (SP) compared to Veterans who screen positive on the primary screen only.	Administrative (CDW) data			
Implementation	Percentage of eligible Veterans sampled at each facility who receive the different stages of VA Risk ID as intended; barriers & facilitators to implementation to fidelity.	EPRP measures			
Level of Evaluation	on: Implementation Strategy				
Effectiveness	Effect of A/F intervention on implementation of VA Risk ID to fidelity compared to IAU alone. Effect of A/F + EF intervention on implementation of VA Risk ID to fidelity compared to A/F alone.	EPRP measures			
Adoption	Number of sites randomized to the implementation interventions that participated. Characteristics of participating/non-participating sites and reasons for participating/not participating.	Key Informant (KI) & Debriefing Interviews			
Implementation	mplementation Percent of sampled instances of implementation intervention delivered to fidelity (i.e., met criteria for adherence).				
Maintenance	Maintenance of adequate implementation following removal of A/F; Sustained implementation of VA Risk ID for high performers	EPRP measures			

Table 1. Application of RE-AIM, Level of Evaluation, Operationalization, and Data Sources

^a All domains will be evaluated at Baseline, Post-Intervention Phase I and II except for maintenance, which will be evaluated at postintervention phase I and II

C2. Design. a. Primary and secondary aims (Effectiveness and Maintenance of the implementation

Figure 2. SMART Design and Intervention Phases

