C5. Randomization. **a. Primary Tailoring Variable (PTV):** The PTV determines the set of randomized intervention options. Thus, the PTV in any SMART must be a proximal measure of the outcome that denotes early success or failure and can be implemented in practice²⁸. In this SMART, the PTV is a predetermined benchmark for adequate implementation. This benchmark will be based on C-SSRS Screener fallouts and CSRE fallouts. The cut-off for both must be 80% or higher (i.e., less than 20% fallouts) to be considered adequate implementation. This cut-off was chosen with input from the program partner and previous QI projects with the program office that involved setting implementation benchmarks (i.e., REACH VET implementation). This benchmark is meant to represent a performance target that all facilities are expected to work towards. Preliminary data indicates that, across facilities since October 2018, the 1st quartile of C-SSRS fallouts is 47.9% (range: 12.9% - 87.4%), and the 1st quartile of the CSRE fallouts is 61.2% (range: 12.5% - 100%). 75% of sites currently have C-SSRS and CSRE fallout percentages greater than 47.9% and 61.2%, respectively. Based on these numbers at least 80-90% of sites currently do not meet criteria for adequate performance. We expect that this number to decrease some as implementation continues, but we expect that many sites will still have significant room for improvement when this project begins. The program partner may adjust this benchmark based on additional data gathered. **b.** Randomization procedures: Randomization will occur at the site level. VAMCs that are not meeting the benchmark for adequate implementation (See PVT above) at Baseline month 6 will be randomized 1:1 (R1) to receive A/F or continued IAU for 10 months. A/F sites that do not meet the benchmark for adequate implementation at the 10th interventional month will be randomized 1:1 (**R2**) to either continue A/F or augmentation with EF (A/F + EF) for an additional 10 months. A/F sites that meet the criteria for adequate implementation will be randomized 1:1 (**R3**) to either continue A/F or discontinue A/F and return to IAU. R1 will be stratified by facility complexity level (i.e., high, medium and low) and level of performance (i.e., low or moderate) at baseline. The Facility Complexity Model²⁹ classifies VA medical facilities at levels 1a, 1b, 1c, 2, or 3. Level-1a facilities are the most complex and level-3 facilities are the least complex. Levels 1a-1c will be considered high complexity, level 2- medium complexity and level 3- low complexity. Approximately 61% of facilities (N=85) are high complexity, 17% (N=24) are moderate and 22% (N=31) are low complexity. Additionally, the average of the C-SSRS Screener and CSRE fallout rates for the 6th Baseline month will be calculated for each facility to be randomized (R1) and the median of these averages will be used to determine stratification by level of performance (i.e., low – above median fallout rate, or moderate – below median fallout rate). R2 will also be stratified by facility complexity level and level of performance (based on the median of the fallout rate at the 10th month of phase 1). R3 will be stratified only by facility complexity level as all sites will have met the benchmark. These procedures will ensure that intervention groups are balanced for site variables that may correlate highly with outcomes. If less than 12 sites will be randomized at R2, stratification will only occur based on facility complexity, unless all facilities are at the same level of complexity in which case only median level of performance will be used for stratification.

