
C7. Analyses. a. Sample Size and Power Calculations: Power was calculated using the two-sample ttest procedure in Power and Sample Size (PASS 16). As there are two primary EPRP outcomes (sui2 and csra1), alpha is set to 0.025. The FY2018 first quarter numbers for a similar EPRP (sre1, timely SRE if positive PTSD or MDD screen) across 140 facilities was used to obtain an estimated standard deviation for sui2 and csra1 of 0.10. Power was calculated for two scenarios given the preliminary fallout data noted above. Assuming proportions of 0.8 and 0.9 not adequately implementing at month 6 of the run-in phase such that N=112 and N=126 are eligible for randomization at R1, this would provide 80% power to detect a difference in change between A/F and IAU of 0.059, and 0.055, respectively. Regarding secondary aim 1, assuming alpha=0.05, SD=0.10, and facilities eligible for randomization at R2 of 56 and 63, there is 80% power to detect a difference in change between continued A/F and A/F + Facilitation of 0.076 and 0.072, respectively. Given the same assumptions for secondary aim 2 as used for secondary aim 1, the detectable differences in change are the same for examining continued A/F versus discontinued A/F. **b. Primary Aim:** Using linear regression, the primary

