Secondary Aim 2a. For sites that responded to AF during Phase 1, determine if switching to AF Light during Phase 2 (January 2022 – July 2023) resulted in a significant decrease in eCSSRS1 and eCSRE1 adherence. To determine the effect of switching to AF Light in Phase 2, we compared Group 2 (Continued AF; N=6) to Group 3 (Switched to AF Light; N=6). We used the same approach as was used for the Primary Aim. Monthly eCSSRS and eCSRE adherence was modeled across the entire study period as a function of group (Continued AF and Switch to AF Light), B-spline transformations on time, and group by B-spline transformation interactions, so that we could estimate a trajectory for each group. Knot selection was the same as for the Primary Aim. Contrasts were constructed within each model and were used to estimate the change in adherence for each group from January 2022 – July 2023 and the difference in adherence change between the groups, which was our hypothesis test of interest. These estimated differences in change were reported with 95% Cls. For both estimates, the difference in change was calculated as the Continued AF group minus the Switch to AF Light group.

Secondary Aim 2b. For sites that did not respond to AF during Phase 1, determine if the addition of External Facilitation (EF) during Phase 2 (January 2022 – July 2023) resulted in a significant increase in eCSSRS1 and eCSRE1 adherence. To determine the effect of the addition of EF in Phase 2, we compared Group 4 (Continued AF; N=38) to Group 5 (Added EF; N=17). We used the same approach as was used for the Primary Aim. Monthly eCSSRS and eCSRE adherence was modeled across the entire study period as a function of group (Continued AF and Added EF), B-spline transformations on time, and group by B-spline transformation interactions, so that we could estimate a trajectory for each group. Knot selection was the same as for the Primary Aim. Contrasts were constructed within each model and were used to estimate the change in adherence for each group from January 2022 – July 2023 and the difference in adherence change between the groups, which was our hypothesis test of interest. These estimated differences in change were reported with 95% CIs. For both estimates, the difference in change was calculated as the Continued AF group minus the Added EF group.

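### SAP Aim 2a compares continued A/F with AF Light at 6 v 6 sites, so it cannot answer the protocol's question about discontinuing A/F, and the detectable differences stated for that aim do not apply to it

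*SAP*

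**What the plan says.** The protocol is consistent about the maintenance question.

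- Specific Aims, secondary aim 2, asks of sites that met the benchmark with A/F alone: "is performance maintained following discontinuation of A/F".
- Table 1 (section C1) defines the maintenance domain for the implementation strategy as "Maintenance of adequate implementation following removal of A/F".
- Section C2 lists Group 3 as improved performers who step down from A/F to IAU.
- Section C5b (R3): "A/F sites that meet the criteria for adequate implementation will be randomized 1:1", the options being "to either continue A/F or discontinue A/F and return to IAU".
- Section C7a gives detectable differences of 0.076 and 0.072 for secondary aim 1, from 56 and 63 sites at R2. It carries them over to secondary aim 2: "the detectable differences in change are the same for examining continued A/F versus discontinued A/F".
- Section C7c plans the same kind of between-group difference analysis for secondary aim 2 as for secondary aim 1.

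The SAP, Secondary Aim 2a, states a different comparison: "we compared Group 2 (Continued AF; N=6) to Group 3 (Switched to AF Light; N=6"). Its aim is to "determine if switching to AF Light during Phase 2 (January 2022 – July 2023) resulted in a significant decrease in eCSSRS1 and eCSRE1 adherence". It estimates each group's change from January 2022 to July 2023 and names the difference in change (continued AF minus AF Light) as the hypothesis test, reported with a 95% CI. The text does not define AF Light, explain the departure from R3, give a margin, or say how a non-significant result should be read.

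**The concern.** There are two separate problems.

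The first is the comparator. The protocol's question needs a group of sites from which A/F was removed. On the SAP's description, one arm kept A/F and the other moved to something called AF Light. No sample size makes that contrast informative about removal.

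The second is sensitivity. A question about maintenance is being addressed by a test for a decrease. Failing to find a decrease says little unless the comparison could have found one of a size that matters. The only sensitivity figures on record for this aim come from a site count about five times the 12 analysed (56/12 = 4.7; 63/12 = 5.3). A reader who takes them at face value would think that a loss of 7 to 8 percentage points would probably have been detected.

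At stake is whether a program office could conclude that A/F can safely be withdrawn from sites that have improved, from data in which no analysed site is described as having had it withdrawn.

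**Working it through.** **Comparator.** Side by side:

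| Source | Arm 1 | Arm 2 |
|---|---|---|
| Protocol, C2 and C5b (R3) | Continue A/F | Stop A/F, return to IAU |
| SAP, Aim 2a | Continued AF (n=6) | AF Light (n=6) |

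The second arms differ, and nothing in the documents equates AF Light with IAU.

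**Inputs for sensitivity.** Two-sample t-test, SD 0.10, alpha 0.05, 80% power, N = 56 or 63 (protocol C7a); 1:1 allocation (C5b); 6 v 6 (SAP Aim 2a).

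**Formula.** SE = SD × √(1/n₁ + 1/n₂); δ = d/SE; df = n₁ + n₂ − 2. Two-sided power is the probability that a noncentral t variable with df and noncentrality δ falls beyond ±t(0.975, df). The detectable difference is the d that gives 80%.

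**Reproducing the plan.**
- N = 56 (28 v 28): SE = 0.10 × √(2/28) = 0.0267; detectable difference 0.0762 (stated 0.076).
- N = 63 (31 v 32): SE = 0.10 × √(1/31 + 1/32) = 0.0252; detectable difference 0.0717 (stated 0.072).
- A one-sided test would give 0.0673 and 0.0634, so the plan used a two-sided test.

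**Feasibility of the planned N.** The counts 56 and 63 are half of the 112 and 126 sites expected at R1, that is, the whole A/F arm. C5b sends A/F sites below the benchmark to R2 and those meeting it to R3, so R2 + R3 = 56 or 63 in total. Both aims cannot have the full number. In the SAP, Groups 2 and 3 give 6 + 6 = 12 and Groups 4 and 5 give 38 + 17 = 55; 12 + 55 = 67, the A/F arm.

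**Same method at 6 v 6.**
- SE = 0.10 × √(2/6) = 0.0577; df = 10; t(0.975, 10) = 2.228.
- Detectable difference at 80% power: 0.180, which is 0.1796/0.0762 = 2.4 times the planned figure.
- At d = 0.076: δ = 0.076/0.0577 = 1.32; power 22%. At d = 0.072: power 20%.
- 95% CI half-width: 2.228 × 0.0577 = 0.129.

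**Range over assumed SDs (6 v 6, two-sided 0.05).** Only SD 0.10 is in the documents.

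| SD | Detectable difference | Power at 0.076 |
|---|---|---|
| 0.05 | 0.090 | 66% |
| 0.075 | 0.135 | 36% |
| 0.10 | 0.180 | 22% |
| 0.15 | 0.269 | 12% |

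The SAP does not state sidedness. A one-sided 0.05 test at SD 0.10 would have 34% power at 0.076 and a detectable difference of 0.154.

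**The case against.** The best defence is that the SAP is candid about what it did. It names the contrast as a switch to AF Light, gives the arm sizes, estimates the change within each arm, and reports the difference with a 95% CI. It nowhere calls a null result maintenance. The difference test was already in the protocol, and the small N follows from only 12 of 67 A/F sites being classed as responders. That cannot now be changed. The figures 0.076 and 0.072 are planning figures that do reproduce at their stated N, and they do not appear in the SAP. All of this stands, and it limits the point to reconciliation and interpretation.

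It also stands that 0.18 and 22% come from a t-test on site-level change, with an SD taken from a different EPRP measure. The SAP fits a spline mixed model with a random site intercept to monthly eCSSRS1 and eCSRE1. Its precision depends on variances that the documents do not give and could differ appreciably.

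What does not stand is that this leaves nothing to correct. The SAP does not say that its contrast departs from R3, define AF Light, or say how a null result should be read. The protocol's sensitivity statement remains the only one on record for this aim.

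**Conclusion.** The point holds in a limited form. SAP Aim 2a does not address discontinuation of A/F, whatever its result, and it must be reconciled with secondary aim 2, Table 1, C2 and R3 in the protocol. The stated 0.076 and 0.072 do not describe the 6 v 6 comparison. On the protocol's own method and SD the figure is about 0.18, with 22% power at 0.076 (0.09 to 0.27, and 66% to 12%, over assumed SDs of 0.05 to 0.15). These numbers are indicative. The conclusion about the comparator does not depend on them. A non-significant result could be misread as maintenance.

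Four stronger readings are tempting but not supported:
- *That a null result is likely, or will be reported as maintenance.* The documents give no results and no such statement.
- *That sites could drop from 80% to 62% (0.80 − 0.18) unnoticed.* The contrast is a between-arm difference in change. It equals that fall only if sites start exactly at 80% and the continued-AF arm stays flat.
- *That a large drop cannot be excluded.* With a half-width of about 0.129, an observed difference of zero would exclude a loss of 0.18. It would not exclude 0.076.
- *That AF Light is a known reduced dose of A/F.* The name suggests it, but the text does not define it.

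**What to change.** 1. In SAP Aim 2a, define AF Light, note that it stands where the protocol planned a return to IAU, and explain the change. State that the aim estimates the effect of switching to AF Light and supports no conclusion on discontinuing A/F.
2. State that 0.076 and 0.072 do not apply to the 6 v 6 comparison. Beside them give about 0.18 with its assumptions (two-sided t-test, SD 0.10, alpha 0.05, 80% power), marked as indicative for the mixed model. Note that R2 and R3 divide one A/F arm, so the full 56 or 63 could not serve both aims.
3. Base the interpretation on the within-arm changes and the 95% CI for the difference, both already planned. Say explicitly that non-significance is not evidence of maintenance.
4. Optionally, report how many of the 6 sites in each arm still met the benchmark in force at the end of Phase 2, as description only. The protocol allows the 80% benchmark to be adjusted, so the value used should be stated.

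The cost is a few sentences and, if wanted, one small table. No new data, model or margin is needed. The downside for the sponsor is that the stated sensitivity and the permitted conclusion both become less favourable.
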